12.3 Missing values and discontinuation of treatment

Handling of missing values and dropouts is to be described and explained in the SAP.

12.4 Analysis sets

The analysis is based on the population of patients with documented administration/prescription of Afinitor[®] for whom at least one follow-up under treatment is available.

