One important objective in the palliative treatment of cancer patients is to enable them to have a good **quality of life** for as long as possible. For this reason, this NIS will examine whether the quality of life under Afinitor[®] changes during the course of treatment. The corresponding questionnaire must be completed by patients in the first and third months after starting treatment and thereafter at 3-month intervals.

The nature and level of physical activity could influence efficacy and/or quality of life of patients with metastatic breast cancer. Such an influence has been shown both for prevention and for the adjuvant setting (Friedensreich 2011). To date however there are hardly any studies that address this issue in metastatic patients. Some data suggest that a **positive effect of physical activity** in women with HR+ breast cancer may be more pronounced than in other breast cancer types (Carmichael et al. 2010). One of the aims of this NIS is to use patient questionnaires to determine the nature and level of physical activity and to investigate a possible correlation with efficacy and quality of life. It will also be used to evaluate whether the fatigue that is present under many therapies can be reduced by physical activity.

Stomatitis is a very common side effect of therapy with Afinitor[®] and exemestane, often occurring soon after starting treatment and frequently regressing during the course of treatment (Porta et al. 2011). In the acute phase, various options are available to the physician to provide relief for the patient. The nature and duration of treatment depend on both the degree of severity of the stomatitis and the specific criteria used by the individual physician. Since the data are as yet unclear, no definitive treatment recommendation for stomatitis under Afinitor[®] can be given. However, stomatitis occurring under treatment with mTOR inhibitors has been seen to differ in nature from the stomatitis that develops under certain chemotherapies. For this reason, this NIS will record the measures used for prophylaxis and, if necessary, treatment of stomatitis and the outcome of these measures.

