6.4.1 Observation parameters at the initial examination

Prerequisite: written consent form for participation in the study

- Date of start of observation/initial examination
- Patient history, demographic data, and characteristics of the disease
 - Date and characteristics of the initial diagnosis (month/year, tumour stage (TNM), grading, histological subtype, Ki67)
 - Diagnosis-specific history at the first evidence of metastasis (date, type of metastasis, location)
 - Previous and current treatment (radiotherapy, pharmacological treatment with start, end, and best result observed with respect to tumour response)
 - Details of previous tumour resection and metastases and their tumour biology if available
- ECOG performance status if conducted
- Height, weight
- Current tumour status (TNM stage, location of metastases and latest imaging (CT, MRI, ultrasound, bone scintigraphy, etc.))
- Reason for switching to Afinitor[®] (progression, patient wish, not progression-induced switch)
- Comorbidity
- Antiresorptive treatment to prevent bone-related complications if bone metastases are present
- Planned prophylactic measures against stomatitis
- Quality of life: patient questionnaire EORTC QLQ-C30/BR23
- Physical activity: "Godin Leisure-Time Exercise Questionnaire" and "Physical Activity Scale" (PAS)
- Compliance: calendar overview provided to estimate treatment compliance
- Prescription for Afinitor[®] (date, dosage, pack size)
- Planned follow-up visit

6.4.2 Observation parameters two weeks after the start of documentation (prospectively after implementation of Amendment 2 in the eCRF)

If a visit takes place approx. 2 weeks after the start of documentation in accordance with routine practice, the following observation parameters are documented at this time:

- Date of follow-up
- Documentation of stomatitis treatment if any was needed and given
- Current tumour treatment with Afinitor[®] (dosage, dose reduction, treatment breaks, reason for dose adjustment)
- Patient questionnaire on stomatitis prophylaxis
- Documentation of adverse events
- Next scheduled follow-up

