6.4.3 Observation parameters at later follow-ups

In accordance with routine practice, documentation of the following observation parameters is to be made at regular follow-up s (e.g. after 1 month, 3 months and thereafter at 3-month intervals):

- Date of follow-up
- ECOG performance status if conducted
- Weight
- Imaging follow-up (not at month 1)
- Evaluation of response to treatment (from imaging and/or clinical assessment of status in accordance with routine practice)
- Current tumour treatment with Afinitor[®] (dosage, dose reduction, treatment breaks, reason for dose adjustment)
- Prophylactic measures relating to treatment management
- Quality of life: EORTC QLQ-C30/BR23 patient questionnaire
- Physical activity: "Godin Leisure-Time Exercise Questionnaire" and "Physical Activity Scale" (PAS)
- Compliance based on a calendar overview, if available
- Documentation of adverse events
- Documentation of stomatitis treatment if any was necessary and given
- Patient questionnaire on stomatitis prophylaxis
- Prescription for Afinitor[®] (date, dosage, pack size)
- Next scheduled follow-up

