12.2 Descriptive statistical methods

Variables reaching at least interval level will be presented in tabular form including their sample values (number of valid and missing values, minimum, maximum, 5th percentile, first quartile, third quartile, 95th percentile, median, mean, standard deviation).

For variables at the nominal and ordinal level, distribution of the absolute and relative frequencies will be indicated.

For adverse events, incidences will be reported based on the patient population included and incidence density (number of events/sum of person times in years) according to the MedDRA system organ class and preferred term for adverse events (AEs), serious adverse events (SAEs), adverse drug reactions (ADRs) and serious adverse drug reactions (SADRs). Times of events and survival time analyses will be analysed using the Kaplan-Meier methodology. The derivation and rating of these event times is described in the SAP.

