12.5 Analysis software

The statistical analysis will be performed using SAS^{\circledast} in the version current at the time of the evaluation.

13 Study reports and publication

The project manager at Novartis and the medical director are responsible for presenting the final report in English within 12 months after completion of the statistical analysis. The results of the study will be published jointly. Before publication by the medical director of the study, Novartis will be entitled to make a statement on the manuscript/abstract.

A progress report based on the classification of the study as a post-authorisation safety study (PASS) will be made at least once a year. The results will be taken into consideration in the periodic safety update report (PSUR) for Afinitor[®]. In the event of relevant findings (safety concerns), the progress report will be submitted to the responsible supervisory authority.

14 Documentation and archiving

The sponsor is responsible for archiving the study documentation for at least 10 years.

According to the MBOÄ (Professional Regulations for Physicians), participating physicians are

obligated to archive the identification list and the documentation of treatment provided in the NIS for

at least 10 years.

15 References

AGO (Arbeitsgemeinschaft für gynäkologische Onkologie) e.V. Kommission Mamma (2012). Diagnosis and Treatment of Patients with Primary and Metastatic Breast Cancer Version 23.03.2012 http://www.ago-online.de/de/fuer-mediziner/leitlinien/mamma/

Baselga J, Semiglazov V, van Dam P, et al. Phase II randomized study of neoadjuvant everolimus plus letrozole compared with placebo plus letrozole in patients with estrogen receptor-positive breast cancer. J Clin Oncol 27:2630-7.

Boyle P, Ferlay J (2005). Cancer incidence and mortality in Europe, 2004, Annals of Oncology; 16: 481–488.

Di Cosimo S and Baselga, J. (2010) Management of breast cancer with targeted agents: importance of heterogeneity. Nat Rev Clin Oncol 7: 139-147.

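### The protocol's only analysis set requires a follow-up under treatment, which can lengthen PFS and understate early fatal and treatment-ending adverse events

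*Protocol*

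**What the plan says.** Section 12.4 defines a single population: "The analysis is based on the population of patients with documented administration/prescription of" the study drug, "for whom at least one follow-up under treatment is available". No safety set or all-treated set appears; ITT occurs only in the list of abbreviations.

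The first opportunity to qualify is loosely timed. Section 6.4.2 makes the early visit conditional: "If a visit takes place approx. 2 weeks after the start of documentation in accordance with routine practice". Section 6.4.3 gives the later follow-ups as "e.g. after 1 month, 3 months and thereafter at 3-month intervals". Section 6.1 says that intervals are not specified.

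The protocol nevertheless collects outcomes for patients who leave treatment before such a visit:
- Section 6.4.4 takes the end-of-treatment record outside the visit schedule, with reason, response and adverse events.
- Section 6.4.5 collects the date of progression or death when treatment stopped before progression.
- Section 7.1 records adverse events up to 30 days after the end of treatment, whatever the causality.

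On analysis, section 12.2 states "Times of events and survival time analyses will be analysed using the Kaplan-Meier methodology" and, for adverse events, "incidences will be reported based on the patient population included". Section 12 leaves the detailed description of the analysis population to the SAP.

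**The concern.** Membership of the set depends on something that happens after treatment starts: being seen at least once while still on the drug. A patient who dies in week 1, progresses clinically in week 3 or stops for intolerability before the first visit does not meet that condition as worded. Removing such patients removes early PFS events from the Kaplan-Meier estimate while keeping later ones.

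PFS in the whole group is part of the primary observation parameter (section 5). Section 4 intends the data to show whether the efficacy seen in the approval study carries over to routine care, including patients whom that study did not include because of prior treatment or state of health. A single-arm figure read against 7.8 months is exposed to any rule that removes early failures.

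On the safety side, section 13 classifies the study as a post-authorisation safety study. Section 4 describes stomatitis as "often occurring soon after starting treatment and frequently regressing during the course of treatment". Early events that kill or end treatment are the ones that the rule can take out of the tables.

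**Working it through.** **The plan's own figures.** The protocol gives no share of patients without a follow-up, so there is no stated figure on this point to reproduce. Its one sample-size statement (section 6.2, more than 11%) does reproduce: 3000/26,000 = 11.5% and 3000/24,000 = 12.5%. The 3000 is used below only to turn percentages into patients.

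**Inputs.** Median PFS m = 7.8 months (sections 4 and 6.3, local evaluation in the approval study), taken as the truth in all treated patients. First follow-up at t0 = 0.5 or 1 month (sections 6.4.2 and 6.4.3). Assumptions: exponential PFS, entry at treatment start, and an assumed share f of patients excluded because of an early PFS event.

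**Upper bound: every patient with an event before t0 is excluded.**
- Hazard: λ = ln 2/7.8 = 0.0889 per month.
- Share with an event before t0: 1 − exp(−λ·t0). Median in the remainder: m + t0.
- 6-month PFS in the remainder: exp(−λ(6 − t0)), against exp(−6λ) = 58.7% in all treated patients.

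| First follow-up | Excluded | Of 3000 | Median | 6-month PFS |
|---|---|---|---|---|
| 0.5 month | 4.3% | about 130 | 8.3 months | 61.3% |
| 1 month | 8.5% | about 255 | 8.8 months | 64.1% |

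**Partial exclusion.** If a share f is excluded for early events, later survival in the remainder is S(t)/(1 − f), so the median solves S(t) = 0.5(1 − f), that is t = −ln[0.5(1 − f)]/λ.

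| f | Of 3000 | Median |
|---|---|---|
| 1% | 30 | 7.91 months |
| 2% | 60 | 8.03 months |
| 3% | 90 | 8.14 months |
| 5% | 150 | 8.38 months |

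**Adverse events.** Incidence in all treated patients = (1 − f)·p + f·q, where p is the incidence in retained patients and q that in excluded patients. All values of p, q and f here are assumed.
- f = 5%, p = 20%, q = 100%: 0.95 × 20% + 5% = 24%. The set shows 20%, too low.
- f = 5%, p = 80%, q = 30%: 0.95 × 80% + 0.05 × 30% = 77.5%. The set shows 80%, too high.
- Discontinuation for adverse events, true rate 10%: if 2 percentage points fall before the first visit and are excluded, the set shows (10 − 2)/98 = 8.2%. If 5 points do, it shows (10 − 5)/95 = 5.3%.

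Overall incidence can therefore move either way. For events that themselves end treatment or life before the first visit, the excluded patients are the cases, and the direction is downward.

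**The case against.** The case for leaving the rule alone has several parts, and some of them stand.

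- **The wording may not exclude these patients.** If the end-of-treatment record counts as a follow-up, most of the loss disappears, and the SAP may say so. However, section 12.4 says under treatment and does not mention that record. A SAP that follows section 12.4 as written carries the exclusion with it.
- **The shift may be small.** This stands. Section 6.4.3 documents no imaging at month 1, and the scheme in section 3 records response only from month 3 or at the end of treatment. Events before the first visit would be mostly deaths and clinical progressions. A reader might infer that PFS is inflated by half a month to a month; the documents do not support that as an estimate.
- **Toxicity stops are not PFS events.** This stands. Dropping patients who stop without progression biases PFS only if their prognosis differs from the rest. Nor does the rule guarantee that retained patients were progression-free at the first visit, only that they were alive and on treatment.
- **Early adverse events stay under surveillance.** This stands for reporting: section 7.2 requires serious events within 24 hours. It does not put them into the incidence tables.
- **Sections 12.2 and 12.4 need not conflict.** A reader might infer a contradiction in the adverse event denominator. The population included can mean all enrolled patients or the section 12.4 set, so the text shows an ambiguity and no more.

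A reader might also take section 4 to rank the early weeks as the most important period for stomatitis. It says only that stomatitis often occurs early.

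Section 12.1 calls all inferential results descriptive. That lowers the stakes, but a descriptive median is still distorted by selecting on early survival.

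**Conclusion.** The point holds as a possible bias of unknown size. Section 12.4 states a rule rather than leaving a detail open: on its literal reading, patients who die, progress clinically or stop before the first follow-up are excluded although their outcomes are collected. For PFS the risk is upward. With 1% to 5% of patients excluded for early events, a 7.8-month median reads as about 7.9 to 8.4 months. The values 8.3 and 8.8 months are upper bounds for first visits at 2 weeks and 1 month. These figures rest on exponential PFS, entry at treatment start and those visit times; because intervals are not fixed, a later first visit would raise the bound.

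For safety, the understatement is secure only for early fatal events and events leading to discontinuation, and only if the section 12.4 set is the denominator. A general fall in adverse event incidence is not established.

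One related selection is separate. Section 6.1 admits patients up to 6 weeks after treatment start. If PFS is timed from treatment start, these patients have survived to consent and were still on treatment then. A wider analysis set does not remove that.

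**What to change.** 1. In section 12.4, define the set for PFS and safety as all consented patients with at least one documented dose, whether or not a follow-up exists.
2. State that end-of-treatment, adverse event, progression and death records all count, and censor patients without later information at last contact.
3. In section 12.2, name this same set as the denominator for adverse event incidence.
4. Report the number of patients without a follow-up under treatment.
5. Keep the follow-up condition only for questionnaire change tables or a sensitivity analysis.
6. If PFS is timed from treatment start, treat entry after treatment start as left truncation at consent, so that each patient joins the risk set only from consent.

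The cost is wording in the protocol and SAP. Items 1 to 5 use records that the plan already collects; item 6 needs the treatment start and consent dates. The downside for the sponsor is that reported PFS may be slightly less favourable.

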12.5 Analysis software

The statistical analysis will be performed using SAS^{\circledast} in the version current at the time of the evaluation.

13 Study reports and publication

The project manager at Novartis and the medical director are responsible for presenting the final report in English within 12 months after completion of the statistical analysis. The results of the study will be published jointly. Before publication by the medical director of the study, Novartis will be entitled to make a statement on the manuscript/abstract.

A progress report based on the classification of the study as a post-authorisation safety study (PASS) will be made at least once a year. The results will be taken into consideration in the periodic safety update report (PSUR) for Afinitor[®]. In the event of relevant findings (safety concerns), the progress report will be submitted to the responsible supervisory authority.

14 Documentation and archiving

The sponsor is responsible for archiving the study documentation for at least 10 years.

According to the MBOÄ (Professional Regulations for Physicians), participating physicians are

obligated to archive the identification list and the documentation of treatment provided in the NIS for

at least 10 years.

15 References

AGO (Arbeitsgemeinschaft für gynäkologische Onkologie) e.V. Kommission Mamma (2012). Diagnosis and Treatment of Patients with Primary and Metastatic Breast Cancer Version 23.03.2012 http://www.ago-online.de/de/fuer-mediziner/leitlinien/mamma/

Baselga J, Semiglazov V, van Dam P, et al. Phase II randomized study of neoadjuvant everolimus plus letrozole compared with placebo plus letrozole in patients with estrogen receptor-positive breast cancer. J Clin Oncol 27:2630-7.

Boyle P, Ferlay J (2005). Cancer incidence and mortality in Europe, 2004, Annals of Oncology; 16: 481–488.

Di Cosimo S and Baselga, J. (2010) Management of breast cancer with targeted agents: importance of heterogeneity. Nat Rev Clin Oncol 7: 139-147.

